Appendix 5: Regulatory, Ethical, and Study Oversight Considerations

Regulatory and Ethical Considerations

This study will be conducted in accordance with the protocol and with the following:

- Consensus ethical principles derived from international guidelines including the Declaration of Helsinki and Council for International Organizations of Medical Sciences (CIOMS) International Ethical Guidelines.
- Applicable International Conference on Harmonisation (ICH) Good Clinical Practice (GCP) Guidelines.
- Applicable laws and regulations.

The protocol, protocol amendments, informed consent form (ICF), Investigator's Brochure (IB), and other relevant documents must be submitted to an institutional review board (IRB)/ethics committee (EC) by the investigator and reviewed and approved by the IRB/EC before the study is initiated.

Any substantial protocol amendments, likely to affect the safety of the subjects or the conduct of the study, will require IRB/EC and regulatory authority (as locally required) approval before implementation of changes made to the study design, except for changes necessary to eliminate an immediate hazard to study subjects or any non-substantial changes, as defined by regulatory requirements.

The investigator will be responsible for the following:

- Providing written summaries of the status of the study to the IRB/EC annually or more frequently in accordance with the requirements, policies, and procedures established by the IRB/EC.
- Notifying the IRB/EC of serious adverse events (SAEs) or other significant safety findings as required by IRB/EC procedures.
- Providing oversight of the conduct of the study at the site and adherence to requirements of 21 Code of Federal Regulations (CFR), ICH guidelines, the IRB/EC, European Directive 2001/20/EC for clinical studies (if applicable), and all other applicable local regulations.

Finances and Insurance

Financing and insurance will be addressed in a separate agreement.

Informed Consent

Prior to starting participation in the study, each subject will be provided with a study-specific ICF giving details of the study treatments, procedures, and potential risks of the study. Subjects will be instructed that they are free to obtain further information from the investigator (or designee) and that their participation is voluntary and they are free to

withdraw from the study at any time. Subjects will be given an opportunity to ask questions about the study prior to providing consent for participation.

Following discussion of the study with study site personnel, subjects will sign the ICF in the presence of a suitably trained member of staff to indicate that they are freely giving their informed consent. A copy of the ICF will be given to the subject.

Subjects must be re-consented to the most current version of the ICF(s) during their participation in the study.

Subject Data Protection

Subjects will be assigned a unique identifier and will not be identified by name in electronic case report forms (eCRFs), study-related forms, study reports, or any related publications. Subject and investigator personal data will be treated in compliance with all applicable laws and regulations. In the event the study protocol, study report, or study data are included in a public registry, all identifiable information from individual subjects or investigators will be redacted according to applicable laws and regulations.

The subject must be informed that his/her personal study-related data will be used by the sponsor in accordance with local data protection law. The level of disclosure must also be explained to the subject. The subject must also be informed that his/her study-related data may be examined by sponsor or contract research organisation (CRO) auditors or other authorised personnel appointed by the sponsor, by appropriate IRB/EC members, and by inspectors from regulatory authorities.

Disclosure

All information provided regarding the study, as well as all information collected and/or documented during the course of the study, will be regarded as confidential. The investigator (or designee) agrees not to disclose such information in any way without prior written permission from the sponsor.

Data Quality Assurance

The following data quality steps will be implemented:

- All relevant subject data relating to the study will be recorded on eCRFs unless directly transmitted to the sponsor or designee electronically (eg, laboratory data). The investigator is responsible for verifying that data entries are accurate and correct by electronically signing the eCRF.
- The investigator must maintain accurate documentation (source data) that supports the information entered in the eCRF.
- The investigator must permit study-related monitoring, audits, IRB/EC review, and regulatory agency inspections and provide direct access to source data documents.
- Labcorp Drug Development is responsible for the data management of this study including quality checking of the data. Predefined agreed risks, monitoring thresholds,

quality tolerance thresholds, controls, and mitigation plans will be documented in a project management plan. Additional details of quality checking to be performed on the data may be included in a data management plan.

- A study monitor will perform ongoing source data verification to confirm that data entered into the eCRF by authorised site personnel are accurate, complete, and verifiable from source documents; that the safety and rights of subjects are being protected; and that the study is being conducted in accordance with the currently approved protocol and any other study agreements, ICH GCP, and all applicable regulatory requirements.
- Records and documents, including signed ICFs, pertaining to the conduct of this study must be retained by the investigator in the study site archive for at least 5 years after the end of the study unless local regulations or institutional policies require a longer retention period. No records may be destroyed during the retention period without the written approval of the sponsor. No records may be transferred to another location or party without written notification to the sponsor.

Investigator Documentation Responsibilities

All individual, subject-specific study data will also be entered into a 21 CFR Part 11-compliant electronic data capture (EDC) system on an eCRF in a timely fashion.

All data generated from external sources (eg, laboratory and bioanalytical data), and transmitted to Labcorp Drug Development electronically, will be integrated with the subject's eCRF data in accordance with the data management plan.

An eCRF must be completed for each enrolled subject who undergoes any screening procedures, according to the eCRF completion instructions. The sponsor, or CRO, will review the supporting source documentation against the data entered into the eCRFs to verify the accuracy of the electronic data. The investigator will ensure that corrections are made to the eCRFs and that data queries are resolved in a timely fashion by the study staff.

The investigator will sign and date the eCRF via the EDC system's electronic signature procedure. These signatures will indicate that the investigator reviewed and approved the data on the eCRF, data queries, and site notifications.

Publications

Publications will be addressed in a separate agreement. The results of this study may be published or presented at scientific meetings. If this is foreseen, the investigator agrees to submit all manuscripts or abstracts to the sponsor before submission. This allows the sponsor to protect proprietary information and to provide comments.

The sponsor will comply with the requirements for publication of study results. In accordance with standard editorial and ethical practice, the sponsor will generally support publication of multicentre studies only in their entirety and not as individual site data. In this case, a coordinating investigator will be designated by mutual agreement.

Authorship will be determined by mutual agreement and in line with International Committee of Medical Journal Editors authorship requirements.

Appendix 6: Schedule of Assessments

Schedule of Assessments – Part A (Single Dose in Healthy Subjects)

Study Procedures	Screening (Day -28 to Day -2)		Treatment Period 1		Follow-up (10 to 14 days postdose)
	Day -1	Day 1 to 4	Days 1 to 4	Day 1 (0 hour)	
Informed consent	X				
Inclusion/exclusion criteria	X	X			
Demographic data	X				
Medical history	X	X ^a			
Urinary drug screen	X	X			
Alcohol breath test	X	X			
Urine cotinine test	X	X			
Serology	X				
Pregnancy test ^b	X	X			
FSH ^c	X				
Height and body weight	X ^d	X			
Study residency:					
Check-in		X			
Check-out			Day 4		
Non-residential visit	X				X
Study treatment administration:					
NST-6179 or placebo			Day 1 (0 hour)		
Pharmacokinetics:					
Blood sampling			Predose, and 0.5, 1, 1.5, 2, 3, 4, 6, 8, 12, 16, 24, 36, 48, and 72 hours postdose		X
Urine sampling			Predose (spot collection) and 0 to 4, 4 to 8, 8 to 12, 12 to 24, 24 to 48, and 48 to 72 hours postdose		
Safety and tolerability:					
Adverse event recording	X	X	Ongoing		X
Prior/concomitant medication monitoring	X	X	Ongoing		X

Schedule of Assessments – Part A (Single Dose in Healthy Subjects)

Study Procedures	Screening (Day -28 to Day -2)		Treatment Period 1		Follow-up (10 to 14 days postdose)
	Day -1	Day 1 to 4	Days 1 to 4	Days 1 to 4	
Clinical chemistry, haematology, and urinalysis	X	X	Predose and 48 hours postdose		X
Coagulation	X	X	Predose and 48 hours postdose		X
Blood pressure, pulse rate, respiratory rate, and oral body temperature	X		Predose, ^c and 1, 2, 4, 6, 8, 12, 24, 36, 48, and 72 hours postdose		X
12-lead ECG	X		Predose, ^c and 2, 4, 12, 24, 48, and 72 hours postdose		X
Telemetry			From at least 1 hour predose to 4 hours postdose		
Continuous 12-lead ECG ^f			3 (triplicate) continuous 12-lead extractions taken prior to dosing, and at 0.5, 1, 1.5, 2, 3, 4, 6, 8, 12, and 24 hours postdose		
Full physical examination	X ^g				
Symptom-directed physical examination			Prior to discharge on Day 4		X
Pharmacogenomics blood sample			Predose ^h		

Abbreviations: ECG = electrocardiogram; FSH = follicle-stimulating hormone.

- a. Interim medical history.
- b. Performed in serum at screening and in urine at all other times. A positive urine pregnancy test will be confirmed with a serum pregnancy test.
- c. Performed in all female subjects (to confirm postmenopausal status).
- d. Height measured at screening only.
- e. Predose assessments will take place within 2 hours prior to dosing.
- f. Monitor for 12-lead ECG recording will be worn from 2 hours predose to 25 hours postdose on Day 1. Prior to dosing, 3 (ie, triplicate) continuous 12-lead extractions are required. The predose extraction timepoints will be averaged for baseline.
- g. Performed between the screening visit and predose assessments.
- h. Optional sample; this sample is not time-sensitive, if not possible to collect predose on Day 1, it can be collected at any time during or after the course of the study.

Schedule of Assessments – Part B (Multiple Dose in Healthy Subjects)

Study Procedures	Screening (Day -28 to Day -2)		Day -1		Days 1 to 16		Follow-up (10 to 14 days post-final dose)
Informed consent	X			X			
Inclusion/exclusion criteria	X		X				
Demographic data	X						
Medical history	X		X ^a				
Urinary drug screen	X		X				
Alcohol breath test	X		X				
Urine cotinine test	X		X				
Serology	X						
Pregnancy test ^b	X		X				X
FSH ^c	X						
Height and body weight	X ^d		X				
Study residency:							
Check-in			X				
Check-out				X			
Non-residential visit	X						X
Study treatment administration:							
NST-6179 or placebo				QD dosing: Day 1 to 14 (0 hour)			
				BID dosing ^g Days 1 to 13 BID (0 hour [AM dose] and 12±0.5 hours later [PM dose]); Day 14 (0 hour [AM dose] only)			

Schedule of Assessments – Part B (Multiple Dose in Healthy Subjects)

Study Procedures	Screening (Day -28 to Day -2)	Day -1	Days 1 to 16	Follow-up (10 to 14 days post-final dose)
Pharmacokinetics:			
QD dosing: Day 1: predose, and 0.5, 1, 1.5, 2, 3, 4, 6, 8, and 12 hours postdose Days 2, 4, 6, 8, 10, and 12: predose Day 14: predose, and 0.5, 1, 1.5, 2, 3, 4, 6, 8, 12, 24, 36, and 48 hours postdose
 
BID dosing: Day 1: pre-AM dose and 0.5, 1, 1.5, 2, 3, 4, 6, 8, and 12 hours postdose (pre-PM dose) Days 2, 4, 6, 8, and 10: pre-AM dose Day 12 and 13: pre-AM dose and pre-PM dose Day 14: pre-AM dose and 0.5, 1, 1.5, 2, 3, 4, 6, 8, 12, 16, 24, 36, and 48 hours postdose
	
Blood sampling			
QD dosing: Day 1: predose (spot collection) and 0 to 4, 4 to 8, 8 to 12, 12 to 24 hours postdose Day 14: predose (spot collection) and 0 to 4, 4 to 8, 8 to 12, 12 to 24, and 24 to 48 hours postdose
 
BID dosing: Day 1: pre-AM dose (spot collection) and 0 to 4, 4 to 8, and 8 to 12 hours postdose Day 14: pre-AM dose (spot collection) and 0 to 4, 4 to 8, 8 to 12, 12 to 24, and 24 to 48 hours postdose
	
Urine sampling (PK for all dose groups and metabolite identification for highest planned QD dose group only)				

Schedule of Assessments – Part B (Multiple Dose in Healthy Subjects)

Study Procedures	Screening (Day -28 to Day -2)	Day -1	Days 1 to 16	Follow-up (10 to 14 days post-final dose)
Blood sampling for metabolite identification (for highest planned dose group only)			QD dosing only: Day 1: predose and 0.5, 1, 1.5, 2, 3, 4, 6, 8, and 12 hours postdose Days 2, 4, 6, 8, 10, and 12: predose Day 14: predose, 0.5, 1, 1.5, 2, 3, 4, 6, 8, 12, 24, 36, and 48 hours postdose	
Safety and tolerability:				
Adverse event recording	X	X	Ongoing	X
Prior/concomitant medication monitoring	X	X	Ongoing	X
Clinical chemistry, haematology, and urinalysis	X	X	Days 1, 4, and 8: pre-AM dose Day 14: 48 hours postdose	X
Coagulation	X	X	Days 1, 4, and 8: pre-AM dose Day 14: 48 hours postdose	X
Fasting lipid panel ^h			Days 1, 7, and 14: pre-AM dose	
Blood pressure, pulse rate, respiratory rate, and oral body temperature	X		QD dosing: Day 1: predose ^e , and 1, 2, 4, and 12 hours postdose Days 2 to 14: predose and 4 hours postdose BID dosing: Day 1: pre-AM dose and 1, 2, 4, and 12 hours postdose (pre-PM dose) Days 2 to 14: pre-AM dose (0 hour) and 4 hours postdose	X

Schedule of Assessments – Part B (Multiple Dose in Healthy Subjects)

Study Procedures	Screening (Day -28 to Day -2)	Day -1	Days 1 to 16	Follow-up (10 to 14 days post-final dose)
12-lead ECG	X		QD dosing: Day 1: predose ^e , and 2, 4, and 12 hours postdose Days 4, 7, and 10: predose Day 14: predose, 2, 4, 12, 24, and 48 hours postdose BID dosing: Day 1: pre-AM dose and 2, 4, and 12 hours postdose (pre PM dose) Day 4, 7, and 10: pre-AM dose Day 14: pre-AM dose and 2, 4, 12, 24, and 48 hours postdose	X
Full physical examination	X ^f			
Symptom-directed physical examination			Prior to discharge on Day 16	X
Pharmacogenomics blood sample			Predose ^j	

Abbreviations: AM = morning; ECG = electrocardiogram; FSH = follicle-stimulating hormone; PK = pharmacokinetic(s); PM = evening.

- Interim medical history.
- Performed in serum at screening and in urine at all other times. A positive urine pregnancy test will be confirmed with a serum pregnancy test.
- Performed in all female subjects (to confirm postmenopausal status).
- Height measured at screening only.
- Predose assessments will take place within 2 hours prior to dosing.
- Performed between the screening visit and predose assessments.
- For BID dosing, the AM and PM dosing time for each subject will be as consistent as possible for each day.
- Only for Cohorts B4 onwards.
- Optional sample; this sample is not time-sensitive, if not possible to collect predose on Day 1, it can be collected at any time during or after the course of the study.

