3.6. Dose Escalation

Doses will be administered in an escalating manner following satisfactory review by the sponsor and investigator of the safety and tolerability data (up to 48 hours post-final dose) and plasma PK data (up to 24 hours post-final dose) from the previous dose group. Doses may be reduced and may be lower than the starting dose. There will be a minimum of 7 days between dose escalations in Part A and a minimum of 14 days between dose escalations in Part B to allow sufficient time for an adequate safety review for each respective part.

Dose escalation in both Part A and Part B will only occur if data from a minimum of 6 subjects have been reviewed from the previous dose group, such that data from a minimum of 4 subjects who have received NST-6179 will be used to make the dose escalation decision.

The justification for this is as follows:

- The study treatment is of a known pharmacological class for which the on-target effects in humans are well characterised. Based upon non-clinical data, no clinically important off-target effects are expected within the proposed dose range.
- A minimum of 4 subjects receiving the active drug is considered sufficient to characterise the safety profile and PK response to NST-6179.

Between each dose escalation, the investigator will review all available data in a blinded manner to ensure it is safe to proceed with the planned dose escalation. An interim safety report, summarising results from all available safety assessments, will be sent to the sponsor prior to the start of each successive group/treatment period. Any clinically significant results will be discussed with the sponsor before dose escalation continues. Interim PK data will also be reviewed in terms of dose escalation and to confirm that the study design remains appropriate. In the event of a disagreement between the sponsor and investigator on the dose escalation decision, the decision of the investigator will be upheld.

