3.7. Dose Escalation Stopping Criteria

The study will be halted if 1 or more subject experience a serious adverse event (SAE) that is considered to be related to IMP or 2 or more subjects in the same group experience severe AEs that are considered to be related to IMP. If, following an internal safety review, the sponsor deems it appropriate to restart the study, this can be done following approval of a substantial protocol amendment. Dosing of subjects, including any ongoing multiple-dose groups, will be stopped immediately if any of the dose escalation stopping criteria are met.

In Part A and Part B, following consultation with the sponsor, dose escalation will stop if:

- Clinically relevant signs or symptoms of similar nature occur in 2 or more subjects in a group that, in the opinion of the investigator, warrant stopping of dose escalation.
- There is evidence of clinically significant increases in liver function tests defined as 3 times the upper limit of normal (ULN) for aspartate aminotransferase (AST), ALT, ALP, or gamma-glutamyl transferase (GGT) or 2 times the ULN for total bilirubin in 2 or more subjects in a group (confirmed with repeat testing).
- Moderate nausea or vomiting that prevents subjects from eating a meal on 3 or more occasions on 2 consecutive days in 2 or more subjects in a group.
- The systemic exposure for any individual subject is predicted to exceed an AUC₀₋₂₄ of 358,000 ng·hr/mL (based on the female cynomolgus monkey at the intermediate dose level of 175 mg/kg/day at Day 28) in the 28-day oral toxicity study and/or a C_{max} of 59,100 ng/mL (based on the female cynomolgus monkey kinetics at the NOAEL [350mg/kg/day at Day 28]).

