4.5. Subject Withdrawal and Replacement

A subject is free to withdraw from the study at any time. In addition, a subject will be withdrawn if any of the following criteria are met:

- change in compliance with any inclusion/exclusion criterion that is clinically relevant and affects subject safety as determined by the investigator (or designee)
- non-compliance with the study restrictions that might affect subject safety or study assessments/objectives, as considered applicable by the investigator (or designee)

- any clinically relevant sign or symptom that, in the opinion of the investigator (or designee), warrants subject withdrawal.

If a subject is withdrawn from dosing, the sponsor will be notified and the date and reason(s) for the withdrawal will be documented in the subject's electronic case report form (eCRF). If a subject is withdrawn from the study, efforts will be made to perform all follow-up assessments, if possible ([Appendix 6](#)). Other procedures may be performed at the investigator's (or designee's) and/or sponsor's discretion. If the subject is in-house, these procedures should be performed before the subject is discharged from the clinic. The investigator (or designee) may also request that the subject return for an additional follow-up visit. All withdrawn subjects will be followed until resolution of all their AEs or until the unresolved AEs are judged by the investigator (or designee) to have stabilised.

Subjects who are withdrawn for reasons not related to study treatment may be replaced following discussion between the investigator and the sponsor. Subjects withdrawn as a result of AEs thought to be related to the study treatment will generally not be replaced.

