7.2.2. Clinical Laboratory Evaluations

Blood and urine samples will be collected for clinical laboratory evaluations at the times indicated in the Schedule of Assessments in [Appendix 6](#). Clinical laboratory evaluations are listed in [Appendix 2](#). The timing of clinical laboratory evaluations may be adjusted and/or additional clinical laboratory evaluations may be performed at other times if judged to be clinically appropriate or if the ongoing review of the data suggests a more detailed assessment of clinical laboratory safety evaluations is required.

Subjects will be asked to provide urine samples for a drugs of abuse screen and cotinine test, and will undergo an alcohol breath test at the times indicated in the Schedule of Assessments

in [Appendix 6](#). For all female subjects, a pregnancy test will be performed at the times indicated in the Schedule of Assessments in [Appendix 6](#).

An investigator (or designee) will perform a clinical assessment of all clinical laboratory data.

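### In Part B the last scheduled liver tests during dosing are at Day 8 predose, so a silent rise that first appears later cannot, from a scheduled sample, stop dosing in the ongoing group

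*Protocol*

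**What the plan says.** **Schedule.** In the Part B table of Protocol Appendix 6, the rows for clinical chemistry, haematology and urinalysis and for coagulation list screening, Day -1, then "Days 1, 4, and 8: pre-AM dose Day 14: 48 hours postdose", then follow-up. Dosing runs to Day 14, either once daily or twice daily with only the morning dose on Day 14. The Day 14 entry is timed 48 hours after that dose, which is Day 16.

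**Stopping rule.** Protocol Section 3.7 lists a liver criterion: 3 times the upper limit of normal (ULN) for AST, ALT, ALP or GGT, or 2 times ULN "for total bilirubin in 2 or more subjects in a group (confirmed with repeat testing". The same section says "Dosing of subjects, including any ongoing multiple-dose groups, will be stopped immediately" when any of its criteria is met.

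**Escalation.** Protocol Section 3.6 requires "satisfactory review by the sponsor and investigator of the safety and tolerability data (up to 48 hours post-final dose" before the next group is dosed.

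**Discretion.** Protocol Section 7.2.2 says "additional clinical laboratory evaluations may be performed at other times if judged to be clinically appropriate". It also permits them when accumulating data point to a need for closer laboratory monitoring.

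**Blood already being drawn.** The once-daily PK row of Appendix 6 includes "Days 2, 4, 6, 8, 10, and 12: predose". The twice-daily row also has pre-AM draws on Days 10 and 12.

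**The concern.** Section 3.7 does two jobs: it holds back the next dose level, and it halts a group that is still being dosed. The second job needs a result that arrives while doses remain. A rise in liver enzymes or bilirubin usually gives the subject nothing to report, so blood tests have to find it. Through the first half of dosing they are 3 and 4 days apart (Days 1, 4 and 8). In the second half no liver test is scheduled at all.

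At stake is the safety of the subjects in the current group. They could go on receiving doses after crossing a limit that the protocol treats as a reason to stop at once. Liver monitoring is relevant to this compound. Section 1.4.1 reports raised ALT at every rat dose level, and Section 1.4.2 reports slight ALT rises in monkeys.

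**Working it through.** **1. Reproduce the plan's own count.** Appendix 3 allows 7 clinical laboratory samples of 7.5 mL per Part B subject. Appendix 6 gives screening, Day -1, Day 1, Day 4, Day 8, Day 16 and follow-up, which is 7; and 7 × 7.5 = 52.5 mL, as stated. No further on-treatment draw is hidden elsewhere.

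**2. Length of the gap.** Day 16 − Day 8 = 8 days.

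**3. Doses at or after the Day 8 predose sample.**
- Once daily: Days 8 to 14 = 7 of 14 (50%).
- Twice daily: Days 8 to 13 give 6 × 2 = 12, plus 1 on Day 14 = 13. The total is 13 × 2 + 1 = 27, so 13/27 = 48%.

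**4. Could another scheduled item fill the gap?**
- The fasting lipid panel (Days 1, 7 and 14, Cohort B4 onwards) holds lipids and apolipoproteins only, according to Appendix 2.
- The escalation review includes Day 16 but concerns the next group.
- Where sentinel dosing is used, the first pair runs at least 72 hours ahead, so with the minimum stagger their Day 16 falls on Day 13 for the other eight. The pair has one active subject and the criterion needs two affected subjects, so this seldom helps.

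**5. What one more sample would do.** Take a predose sample on day *d*. The longest gap is the larger of *d* − 8 and 16 − *d*.

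| Last on-treatment sample | Gaps after Day 8 (days) | QD doses at or after it | BID doses at or after it |
|---|---|---|---|
| Day 8 (as planned) | 8 | 7 | 13 |
| Day 10 | 2 + 6 | 5 | 9 |
| Day 12 | 4 + 4 | 3 | 5 |

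**6. Doses still stoppable after a confirming repeat.** Laboratory turnaround is not stated, so it is assumed to be same-day, next-day or 2-day. The repeat is drawn on the morning the first result is known (the next morning if the result is same-day). A confirmed stop then takes effect from day *d* + 1, *d* + 2 or *d* + 4. Once-daily doses left are 14 − *d*, 13 − *d* or 11 − *d*, and never below 0.

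| First abnormal sample | Same-day | Next-day | 2-day |
|---|---|---|---|
| Day 8 | 6 | 5 | 3 |
| Day 10 | 4 | 3 | 1 |
| Day 12 | 2 | 1 | 0 |
| Day 16 | 0 | 0 | 0 |

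**7. Blood volume (Appendix 3).** With one more 7.5 mL sample:
- Table without metabolite sampling: 152.1 + 7.5 = 159.6 mL (cap 190 mL).
- Metabolite group: 214.6 + 7.5 = 222.1 mL (cap 270 mL).
- With a 7.5 mL repeat as well: 167.1 mL and 229.6 mL.

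**The case against.** The strongest reply is that the risk is small and the protocol is already flexible.

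- **Exposure.** Half-life is about 1 to 3 hours and the Day 14 to Day 1 AUC ratio is 1.13 to 1.21 (Protocol Tables 6 and 7), so Days 4 and 8 already sample near-plateau exposure.
- **Signals.** Rat liver findings were reversible and none was judged adverse. Monkey ALT rose by 10.6% to 24.1%, far from 3 times ULN. Section 1.6.1.2 reports no clinically significant laboratory changes up to 1000 mg once daily for 14 days.
- **Oversight.** Subjects are resident, are asked about their condition at least daily, and have vital signs taken on each dosing day. Section 7.2.2 lets the laboratory timing be adjusted as well as tests added.
- **Limits of the remedy.** Day 10 is only two days after Day 8, and the group rule still needs two subjects over a limit.

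Most of this stands, and it sets the priority low. It does not close the gap. Discretionary testing needs a prompt, such as an adverse event, a Day 8 trend or a finding in an earlier group. A first silent rise after Day 8 gives none. Flat exposure does not exclude an effect that depends on time. The monkey values are reported at Week 4 with no earlier on-treatment value, so they do not show when a rise would begin.

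Three stronger readings are tempting, and the documents do not support them.

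- A reader might infer that no safety laboratory sample of any kind is taken during dosing after Day 8. From Cohort B4 a Day 14 predose lipid panel is scheduled; only liver tests are absent.
- A reader might infer that escalation proceeds without late liver data. Day 16 is inside the 48-hour review.
- A reader might infer that the protocol breaks its own rule. Section 3.7 says what follows when a criterion is met; it does not promise chemistry up to the last dose.

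**Conclusion.** The point holds for the planned 14-day schedule and for scheduled samples. A liver-test rise that is silent and first appears after Day 8 cannot trigger the immediate stop in the group being dosed. The unsampled stretch is 8 days and covers 7 of 14 once-daily or 13 of 27 twice-daily doses. A Day 8 abnormality can still be acted on while doses remain, and the next dose level is protected. The likelihood of harm is low on the data reported, so this is worth considering as a cheap improvement; it does not undermine the study.

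The dates and dose counts rest on Appendix 6 alone. The stoppable-dose figures also rest on the assumed turnaround.

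On applicability, SAP Section 1 says that protocol Version 5 was never used for study conduct. The change log describes the Version 5 edit to these rows only as a pre-AM clarification, so the sampling days are taken to be the same in Version 4. Groups B1 to B3 are reported as complete, so the value lies in any further multiple-dose group or any study that reuses this schedule. Section 3.1.2 allows dosing for up to 28 days, but no schedule for that is given and nothing is concluded about it here.

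**What to change.** 1. In Appendix 6, Part B, add clinical chemistry at Day 10 pre-AM dose on the PK venepuncture already scheduled then. The existing row combines chemistry, haematology and urinalysis, so use a footnote or split the row.
2. State that any on-treatment value over a Section 3.7 liver limit is repeated promptly, for example within 24 hours as an unscheduled draw under Section 7.2.2, without waiting for the next PK draw.
3. Raise the clinical laboratory count from 7 to 8 in both Part B tables of Appendix 3.

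The Day 8 and Day 16 samples and the escalation review stay as they are. A clinically significant Day 10 result in one subject could also be acted on individually. Section 4.5 provides for withdrawal on "any clinically relevant sign or symptom that, in the opinion of the investigator (or designee), warrants subject withdrawal", and Appendix 1 counts a clinically significant abnormal laboratory finding as a sign.

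Day 12 predose with the same prompt repeat is an acceptable alternative. It splits the gap evenly but leaves fewer doses to stop: 2, 1 or 0, against 4, 3 or 1 for Day 10 (once daily, same-day, next-day or 2-day turnaround).

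**Cost.** No extra visit or scheduled venepuncture is needed, though a repeat would need its own draw. The extra blood is at most 7.5 mL, since that volume also covers pregnancy and FSH tests; the totals stay within both caps. The downsides are one more fasted sample, one more set of results to review, and one more chance of an incidental abnormal value that needs repeating. A rise that first appears after Day 10 would still be found on schedule only at Day 16.
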